10. DATA COLLECTION AND QUALITY ASSURANCE

10.1 Data Collection Forms

The Controlled Substance Utilization Review and Evaluation System (CURES) will provide records of opioids dispensed at California pharmacies attributable to each provider in our sample treating all civilian, non-Veteran’s Administration and non-institutionalized patients. CURES is California’s prescription drug monitoring program. The Medical Examiner has authority to use CURES for the purpose of educating practitioners and others in lieu of disciplinary, civil, or criminal actions, in accordance with the California State’s Health and Safety Code § 11165(c)(2). First name, last name, date of birth and address identified each decedent in the medical examiner reports and CURES data. Drug Enforcement Agency (DEA) number identified the prescribers in CURES data. Data from eligible clinicians will be extracted from CURES and kept onsite at the medical examiner’s office for de-identified analytic file preparation. A file stripped of patient and clinician identifiers will be prepared and released for analysis on secure servers at the University of Southern California.

10.2 Data Management

Each of the participating sites will create an extract from the CURES database for all deceased patients where prescription drug over-dosage was the primary cause or contributed to the cause of death. These records will be accessed, extracted, then transferred to the localized database in the coordinating center on a weekly basis. The coordinating center has created programs and quality control queries for transforming all of the data into a standard model (Observational Medical Outcomes Partnership Common Data Model, version 3). The data collection forms will be CURES database extracts.

10.3 Quality Assurance

10.3.1 Training

All project personnel handling study data will be certified by the Collaborative IRB Training Initiative (CITI) program, which consists of courses in the Protection of Human Research Subjects for Biomedical Research. Staff will be trained on the permissible values present in the CURES database, frequency of update, and expected volumes of data.

10.3.2 Quality Control Committee

The quality control committee consisted of practicing clinicians from each participating clinical organization. They reviewed automatically refreshing dashboards for potential deviations in coding systems and appropriate values for codes included in the outcome measures. These dashboards were reviewed prior to each email distribution.

10.3.3 Metrics

Quality control metrics were based on reports based on verifications for prescription with National Drug Codes for Schedule II/III/IV drugs following the FDA Drug Schedule.

10.3.4 Protocol Deviations

Our task tracking system, JIRA was used to track and document issues. Each issue included an assignee and a reviewer.

10.3.5 Monitoring

In addition to data quality reviews, we will also review the integrity of the interventions. It is the primary role of the data analysts to: 1) determine the appropriate number of eligible providers to reach sufficient statistical power, 2) record provider information in a secure, password protected database located at LA County Medical Examiner-Coroner's office and, 3) track enrolled providers in regards to their intervention status and progress. On an approximately quarterly basis, staff would visit headquarters of participating sites and verify functionality of decision support tools. Additionally, practicing clinicians on our study team had the ability to monitor electronic medical record interventions in their own health systems.

11. PARTICIPANT RIGHTS AND CONFIDENTIALITY

11.1 Institutional Review Board (IRB) Review

The study protocol will be reviewed and approved by the University of Southern California's Institutional Review Board (IRB). Individual site protocols will also be submitted for review and approval by the California site local IRB.

11.2 Informed Consent Forms

We will request a waiver of consent.

11.3 Participant Confidentiality

Data will be recorded on a localized data warehouse. Data will be kept in encrypted files on computers in locked offices at San Diego County Medical Examiner's Office facilities. Only study investigators will have password protected access to a restricted patient and prescriber information.

11.4 Study Discontinuation

Following each DSMB meeting, the board will make recommendations to the local IRBs as to whether the study should continue or if changes to the protocol are necessary for continuation.

12. COMMITTEES

Not applicable

13. PUBLICATION OF RESEARCH FINDINGS

Publication of results from our research will follow the NIH Public Access Policy, which requires that we submit to the National Library of Medicine's PubMed Central an electronic version of final, peer-reviewed manuscripts upon acceptance for publication, to be made publicly available no later than 12 months after the official date of publication.

15. SUPPLEMENTS/APPENDICES

OPIOIDS LIST

Included	Excluded
Codeine	Buprenorphine
Fentanyl tablet	Butorphanol

Fentanyl patch	Dihydrocodeine
Hydrocodone	Fentanyl lozenge
Hydromorphone	Fentanyl powder*
Methadone	Fentanyl spray*
Morphine	Levorphanol tartrate
Oxycodone	Meperidine
Oxymorphone	Opium
Tapentadol	Tramadol

*Excluded because prescription was likely administered in office by a healthcare professional

List taken from CDC Commonly Prescribed Opioids

<https://www.cdc.gov/mmwr/volumes/65/rr/rr6501e1.htm>

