9.4 Outcomes

9.4.1 Primary outcome

Our primary analysis assesses changes over time before and after the intervention in natural log-transformed MME between treatment and control.

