9.4.2 Secondary outcomes

As secondary hypotheses, we evaluate if the intervention cohort had 1) fewer high-dose opioid prescriptions (≥ 50 or > 90 MME per day), or 2) fewer new patients who were started on opioids. High-dose prescriptions were evaluated using censored regression on percent of clinician fills on high-dose. Chance of a fill being a “new start” were evaluated using logistic regression. These analyses were also conducted within a difference-in-differences framework.

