9.5 Data Analyses

Descriptive and inferential statistics will be carried out in STATA (Version 14.0; Stata Corporation, College Station, TX). The *cmp* command in STATA will be used to compute a difference-in-differences estimator within a mixed-model censored linear regression.(17) The difference-in-differences estimator compares the average change over time in MME dispensed for prescribers in the intervention group, compared to the average change over time for prescribers in the control group. The natural log transformation of MME ensures normally distributed data. Censored regression has a continuous component and a discrete one. Natural log MME doses estimated over days where opioids were dispensed in the name of a prescriber represent the continuous part, and days with no opioids filled in that prescriber’s name represent the discrete part of the model. We denote estimation of the dependent variable as $\log(\overline{MME})^*$ to distinguish it from uncensored estimation. The analysis is represented by:

$$\log(\overline{MME})^*_{ijk} = \beta_1 x_{1ij} + \beta_2 x_{2ij} + \beta_3 x_{3ij} + \delta_{i(k)} \quad [1]$$

where β_1, β_2 and β_3 are fixed effects coefficients on time, x_1 , intervention, x_2 , and time by intervention interaction, x_3 , respectively. Alphabetic subscripts describe the i th prescriber, j th prescription filled and k th decedent, the nested random intercept $\delta_{i(k)}$ is normally distributed with mean zero and variance, $\sigma_{i(k)}^2$, for each i prescriber nested in (i.e., having prescribed to) decedent $k, i(k)$. With natural log transformed data, the value $100 \cdot [\exp\{\beta_3\} - 1]$ measures the percentage change in MME attributable to the intervention when data are uncensored.(18) However, when data are censored the coefficient β_3 must be adjusted to reflect the effect on the observed outcome. We will evaluate data 3 months pre-intervention and 3 months post-intervention, with

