post-intervention beginning one month after the letter was sent to washout contamination by prescriptions written before receipt of the letter but filled afterwards. For the one-year analysis we will include a regressor to control for the 3-month effect. We will perform sensitivity analysis on regression assumptions. As secondary hypotheses, we evaluate if the intervention cohort had 1) fewer high-dose opioid prescriptions (≥ 50 or > 90 MME per day), or 2) fewer new patients who were started on opioids. High-dose prescriptions will be evaluated using censored regression on percent of clinician fills on high-dose. Chance of a fill being a “new start” will be evaluated using logistic regression. These analyses will also be conducted within a difference-in-differences framework.

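### If the appendix opioid list defines MME, switching caused by the letter to tramadol or another excluded opioid would count as a reduction, and no planned analysis would show it

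*Combined protocol and SAP*

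**What the plan says.** Section 9.4.1 makes the primary outcome the change over time in "natural log-transformed MME between treatment and control". Section 9.5 estimates it by difference-in-differences in a censored mixed model that "compares the average change over time in MME dispensed for prescribers in the intervention group" with the corresponding change among controls. The continuous part of the model is log MME on days with opioid dispensing. The discrete part is "days with no opioids filled in that" prescriber's name.

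Section 15 gives the only opioid list in the plan. Its ten excluded entries are buprenorphine, butorphanol, dihydrocodeine, fentanyl lozenge, fentanyl powder, fentanyl spray, levorphanol, meperidine, opium and tramadol. An asterisk on fentanyl powder and fentanyl spray leads to the note "Excluded because prescription was likely administered in office by a healthcare professional". The other eight carry no mark. Below the note stands "List taken from CDC Commonly Prescribed Opioids".

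The secondary hypotheses in section 9.4.2 include "fewer new patients who were started on opioids", with no rule for what counts as prior use. On robustness, section 9.5 says only: "We will perform sensitivity analysis on regression assumptions".

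**The concern.** The letter reports a patient's death and asks for more careful opioid prescribing. One plausible response is to prescribe less. Another is to prescribe a different opioid. If the replacement is an excluded product, the fill leaves the measured outcome although the patient still receives an opioid.

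Randomisation and difference-in-differences do not protect against this. Switching common to both arms cancels. Switching caused by the letter occurs in the letter arm after mailing, which is exactly the contrast that the interaction term estimates.

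At stake is the meaning of a positive result: less opioid prescribing, or less prescribing of the ten listed products with part of it moved elsewhere. The check for reductions above 20% in sections 7.1 and 7.6 has the same ambiguity, since it refers to opioid prescribing and MME without saying which products count.

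**Working it through.** **1. What the list justifies.** Ten products are excluded and two carry the in-office reason, so 10 − 2 = 8 have no reason stated in the plan, tramadol among them. The citation gives the origin of the list. It does not say why a dispensed opioid should be left out of a trial of prescribing behaviour.

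**2. How an excluded fill enters the primary model.** Take the section 15 list as the definition of an opioid and read it into section 9.5. A day with listed and excluded fills contributes only its listed MME to the continuous part. A day with excluded fills alone goes to the zero part. Either way, moving a fill from a listed to an excluded product lowers the measured outcome.

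**3. How much of a measured fall could be real.** The documents give none of the quantities needed, so these are assumptions:
- s: share of listed MME moved to excluded opioids by the letter
- r: fraction of that morphine equivalence kept by the replacement, taken between 0 and 1
- e: baseline excluded MME as a fraction of listed MME

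With listed MME set to 1 at baseline and no other change:
- listed MME goes from 1 to 1 − s, a measured change of −s
- all-opioid MME goes from 1 + e to 1 + e − s(1 − r), a change of −s(1 − r)/(1 + e)

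For an assumed s = 0.05 the measured change in total listed MME is −5.0% in every cell below. The all-opioid change is:

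| r | e = 0 | e = 0.2 |
|---|---|---|
| 1 | 0.0% | 0.0% |
| 0.5 | −2.5% | −2.1% |
| 0.25 | −3.75% | −3.1% |
| 0 | −5.0% | −4.2% |

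For example, at r = 0.5 and e = 0.2: −0.05 × 0.5 / 1.2 = −0.021. The same measured fall is therefore compatible with no change in all-opioid MME or with a change as large as the one measured.

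**4. What this does not give.** The table concerns totals. The planned coefficient is on log MME in a censored model, and section 9.5 itself says that it must be adjusted to describe the observed outcome. If every dispensing day loses the same 5%, each observed log value moves by ln(0.95) = −0.051. If the same 5% of MME is lost by emptying whole days, the remaining days do not change and the censored share rises, so the coefficient moves by an amount that depends on the dose distribution. A share of MME moved does not translate into a fixed coefficient.

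**5. Secondary outcomes.** If the same list is used, a patient started on tramadol is not seen as a new start, and a patient who moves from tramadol to a listed opioid may be counted as one. The outcome is the chance that a fill is a new start, so the denominator changes as well and the direction of any bias is not fixed.

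**6. Planned safeguards.** The one sensitivity analysis named concerns regression assumptions. No outcome or sensitivity analysis in sections 9.4 and 9.5 examines excluded opioids or switching.

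**The case against.** Several objections have force.

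- **The link is inferred.** The list is headed only as a list of opioids, and no section ties it to MME, to zero days or to new starts. That stands. For MME it is still the natural reading, since this is the only list and its footnote explains why prescriptions were dropped. For new starts the link is weaker.
- **A source is cited.** This is true, and whether that source explains the eight exclusions cannot be checked from the documents. The plan itself does not reproduce a reason.
- **Switching is undocumented.** None of the five strategies in the letter (section 5.1) recommends another opioid, and no section reports switching or volumes. That tramadol is in the extract at all is inferred from its place on the list and the Schedule II–IV scope. So the bias is possible, not shown.
- **Some switching is real reduction.** If the replacement carries less morphine equivalence, part of the measured fall serves the objective in section 1.1.
- **Some of the data are already planned.** Section 6.1 collects scheduled-drug prescriptions separately from MME, and section 3 names their number as the primary aim. But that count is not specific to opioids, and sections 9.4 and 9.5 do not analyse it.

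A reader might go further and infer that a given share switched would produce the same share of the planned 5% effect. The documents do not support that. The 5% in section 9.2 is a difference in means paired with a standard deviation in daily MME, not a coefficient on log MME, and the inference also assumes a replacement that keeps its full morphine equivalence. Nor do they support saying that the result is biased in favour of the letter. They support only that it could be, if the letter causes switching.

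**Conclusion.** The point holds as a conditional weakness in the outcome definition. If the section 15 list defines MME, and if the letter moves some prescribing to excluded opioids, the primary estimate overstates the fall in opioid prescribing. It does so entirely when the replacement keeps the same morphine equivalence and nothing else changes, and less when the replacement carries less. No size can be given, because the documents contain neither the volume of excluded opioids nor the extent of switching. The figures in the table are illustrations under assumed values. The issue does not touch the sample size or the choice of primary model. It should be addressed because the plan has nothing that would reveal substitution, and dispensing data from the same source could.

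**What to change.** 1. State which outcomes use the section 15 list (MME, zero-opioid days, high-dose share, new starts, the 20% safety check), and give the reason for the eight unmarked exclusions.
2. Pre-specify a difference-in-differences comparison of fills of excluded pharmacy-dispensed opioids, by drug and as counts, over the same pre- and post-letter windows as the primary analysis. Counts need no conversion factor.
3. Pre-specify one sensitivity run of the primary model that adds tramadol and the other excluded pharmacy-dispensed analgesic opioids with an accepted conversion factor. Leave out the two asterisked fentanyl forms and report buprenorphine separately.
4. Define a new start, and add a sensitivity analysis in which any earlier opioid fill in the CURES extract, listed or not, counts as prior use.
5. Describe the primary result as a change in listed opioids unless these analyses show no material substitution.

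The cost is SAP wording, one or two extra runs on CURES dispensing data, and the choice of conversion factors, which is open to argument and should be fixed in advance. If the extract does not hold an excluded product, the plan should say so, and that product's substitution remains unexamined.
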